6.9.2. Prior and Concomitant Medication

In case of missing or partially missing start dates (resp. stop date) for prior/concomitant medication, same rules as those described in Table 10 (resp. Table 11) for AE will be applied.

6.9.3. Initial Diagnosis Date

In case of missing or partially missing dates for initial diagnosis, the following rules will be applied:

- If initial diagnosis date=../mmm/yyyy (= missing day), then it will be substituted by **01/mmm/yyyy**
- If initial diagnosis date=.../.../yyyy (= missing day and month), then it will be substituted by **01/JAN/yyyy**
- If initial diagnosis date=.../.../.... (= completely missing), then it won't be substituted.

Same applies for missing or partially missing dates for first metastasis.

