6.5. Appendix 5: Cancer History

Cancer History will be summarized in participants from the SAF and the DDS (if different from the SAF). Cancer History will also be listed for the SAF.

Note:

- In case of missing initial diagnosis date or missing date of first metastasis, substituting rules defined in appendix 9 (Section 6.9.3) will be applied.

The Cancer History data are described in the Table 9 below:

Table 9: Cancer History data

Variable	Quantitative parameters	Qualitative parameters	Derived variable	SAF	DDS*
Diagnosis at study entry		X	X	X	X
Time since initial diagnosis (months) computed as [date of treatment assignment minus the date of initial diagnosis + 1]/30.4375	X		X	X	X
Primary tumor location		X		X	X
Delay between diagnosis of the primary tumor and metastasis (months)	X		X	X	X
Diagnosis method		X		X	X
Metastatic disease sites ("List of metastatic organs")		X		X	X
Number of metastatic organs (1, 2, >2)		X		X	X
Number of Prior Systemic Regimens in the metastatic setting	X			X	X

*: If different from the SAF

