6.9. Appendix 9: Missing Values – Missing Visits

For partially missing dates for efficacy endpoints, the following imputation rules will be used: if the day of the month is missing, but month and year are known (UN-MMM-YYYY), it will be imputed by the 1st of the month (01-MMM-YYYY). If this implementation rule produces a date before start of treatment, then the date of start of treatment is used.

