6.9.4. Antineoplastic therapies

Prior Antineoplastic therapies

Incomplete start dates will be handled by applying the same imputation rules as described for AE/concomitant medications start date (Sections 6.9.1 and 6.9.2) except:

- If only day is missing, and month and year match that of the treatment start date, impute as first dose of study -1;
- If both day and month are missing, and the year matches that of the treatment start date, then impute as date of first dose of study drug - 1.

Completely missing start date is imputed as date of first dose of study drug - 1;

Incomplete end dates and dates of progression on the prior antineoplastic therapies will be handled using the following rule:

- If only day is missing, imputed date = min (date of first dose of study drug -1, last day of the month);
- If both month and day are missing, imputed date = min (date of first dose of study drug -1, 31DEC).
- If the end date or the date of progression is not missing and the imputed start date is after the end date or after the date of progression, use the min (end date, date of progression) as the imputed start date.

Post-treatment therapies:

If any, it will be reported as part of the concomitant medications, and handled as specified in Section 6.9.2.

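### The SAP 6.9.3 rule for a partial first-metastasis date has no floor at initial diagnosis, so the diagnosis-to-metastasis delay in Table 9 can become negative

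*SAP*

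**What the plan says.** SAP 6.9.3 covers the initial diagnosis date in three cases. For a missing day: "If initial diagnosis date=../mmm/yyyy (= missing day), then it will be substituted by" the 1st of the recorded month. For a date with "missing day and month), then it will be substituted by" 1 January of the recorded year. A completely missing date is left missing. The section closes with "Same applies for missing or partially missing dates for first metastasis".

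SAP 6.5 sends both dates to that rule and to no other: "In case of missing initial diagnosis date or missing date of first metastasis, substituting rules defined in appendix 9 (Section 6.9.3) will be applied". Table 9 in the same section lists "Delay between diagnosis of the primary tumor and metastasis (months") as a quantitative, derived variable. It gives no formula for this row, although it gives one for time since initial diagnosis. On reporting it says: "Cancer History will be summarized in participants from the SAF and the DDS (if different from the SAF"). SAP 5.1 sets the statistics for continuous data: mean, standard deviation, median, quartiles, minimum and maximum.

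Two other rules in the same appendix do protect the order of dates. For efficacy dates, SAP 6.9 says: "If this implementation rule produces a date before start of treatment, then the date of start of treatment is used". For prior anticancer therapy, when the imputed start falls after a known end or progression date, SAP 6.9.4 says: "use the min (end date, date of progression) as the imputed start date". Neither applies to the diagnosis and metastasis dates.

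**The concern.** Diagnosis of the primary tumor and first metastasis are ordered: the second should not precede the first. A rule that picks the earliest possible date is harmless for the earlier event, where it can only lengthen the interval. Applied to the later event, it can pull that event back past the earlier one.

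Every participant must have metastatic melanoma or NSCLC (Protocol 5.1). Where metastases are found at or soon after first diagnosis, both dates fall in the same month or year, which is one of the two conditions for an impossible value. The design plans three evaluable participants, expandable to six, so there is little data to dilute one such value. At stake are the printed mean and minimum of one baseline characteristic, and the credibility of a table that shows metastasis before the primary tumor.

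**Working it through.** The plan states no figure here, so there is none to reproduce. The check applies the 6.9.3 rule to pairs of dates.

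**Inputs.** The substitution rule is from SAP 6.9.3. The divisor 30.4375 days per month is the one Table 9 uses for time since initial diagnosis. The formula is an assumption, because Table 9 gives none for this row: delay = (metastasis date - diagnosis date) / 30.4375, after imputation. A variant adding 1 day, as the neighbouring row does, was also run.

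**When the delay turns negative.**

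- *Case A: diagnosis complete, metastasis day missing, same month.* With diagnosis on day d of the month, the difference is 1 - d days, negative for any d after the 1st. The lowest value is 1 - 31 = -30 days, or -30 / 30.4375 = -0.99 month.
- *Case B: diagnosis complete, metastasis year only, same year.* With diagnosis on day k of the year, the difference is 1 - k days, negative after 1 January. The lowest value in a 365-day year is 1 - 365 = -364 days, or -11.96 months.
- *Case C: diagnosis missing the day only, metastasis year only, same year.* Diagnosis becomes the 1st of its month and metastasis becomes 1 January. The delay is negative for any diagnosis month after January. The lowest value is from 1 December: -334 days, or -10.97 months.

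In every other pairing the delay is never negative: both dates equally partial, the diagnosis date the less complete one, or metastasis in a later recorded month (day missing) or later year (day and month missing).

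**How often, given the pattern of missing parts.** Diagnosis was spread evenly over a 365-day year and the true lag evenly over the stated range. Both are assumptions.

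| True lag | A: negative | B: negative | C: negative |
|---|---|---|---|
| 0 days | 96.7% | 99.7% | 91.5% |
| 0-30 days | 47.5% | 95.6% | 87.4% |
| 0-364 days | 4.0% | 49.9% | 42.0% |
| 366-730 days | 0% | 0% | 0% |

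Adding 1 day changes these by at most about 3 percentage points.

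**Worked examples (dates chosen for illustration).**

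- Diagnosis 15 March 2021, metastasis recorded as March 2021: imputed 1 March, -14 days, -14 / 30.4375 = -0.46 month.
- Diagnosis 15 October 2021, metastasis recorded as 2021: imputed 1 January, -287 days, -287 / 30.4375 = -9.43 months. If the true delay is zero, the mean shifts by -9.43 / 3 = -3.14 months with three participants, or -9.43 / 6 = -1.57 months with six. The minimum becomes -9.43.

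**With a floor at diagnosis.**

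- Diagnosis 20 March 2020, metastasis March 2020: -0.62 becomes 0.00 month.
- Diagnosis 20 September 2020, metastasis 2020: -8.64 becomes 0.00 month.
- Diagnosis 20 September 2020, metastasis 2021: 3.38 months, unchanged.

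The floor removes impossible values, not all imputation error. In the second example, a true metastasis date of 10 November 2020 would give 1.68 months, against 0.00 after the floor.

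**The case against.** A reader might infer that the rule routinely dates metastasis before the primary tumor, or that it fails whenever disease is metastatic at diagnosis. The documents do not support either reading. Sharing a month or year is not enough; the metastasis date must also be the less complete of the two. If simultaneous findings are recorded with equal precision, the rule gives exactly zero, which is correct. Nothing in the documents says how often dates are partial, or that metastasis dates are recorded less precisely. The percentages above apply only within the failing patterns of missing parts and are not expected rates for this study.

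The comparison with neighbouring rules should not be pressed either. SAP 6.9.1 and 6.9.2 state no start-before-end check in their examples, and the 6.9 floor serves efficacy dates. The missing guard is a gap, but not unique in the appendix.

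Other controls may catch the case. Protocol 10.1.8.3.3 provides edit checks and queries, Protocol 10.1.8.3.5 requires data review before lock, output specifications sit outside the SAP (SAP 6.3), and cancer history is also listed by participant. SAP 6.2 allows some protocol-planned summaries to become listings. These points are fair, but none of these provisions states the floor, and SAP 6.5 still commits to summarising this variable.

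Materiality is low. The study is descriptive, the delay enters neither the DLT analysis nor the steering committee's stated tolerability criteria, and the median and quartiles resist one outlier better than the mean. That stands.

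**Conclusion.** The point holds as a conditional one. As written, SAP 6.9.3 can produce an impossible negative delay, down to about -1 month with the day missing and about -12 months with day and month missing. This needs a metastasis date less complete than the diagnosis date, within the same recorded month or year. The existence of the problem follows from the rule alone. The sizes rest on the assumed delay formula, and the frequencies also on evenly spread dates and lags. The overall likelihood cannot be estimated from the documents.

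The effect is confined to the mean and minimum of one descriptive baseline variable. It appears in the safety set, and in the dose-determining set only if that set differs. The safety set can exceed six, because non-evaluable treated participants are replaced but stay in it, so the dilution may be somewhat greater than the n = 6 figure suggests. A reader might infer a threat to the primary result. There is none: DLT incidence does not use these dates. This is a minor correction worth making because it costs almost nothing.

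**What to change.** Add to SAP 6.9.3: *If the recorded part of a partial first-metastasis date is compatible with a date on or after initial diagnosis, it is imputed as the later of the date given by this rule and the (imputed) date of initial diagnosis; a recorded month or year earlier than diagnosis is queried and not overwritten.*

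The compatibility condition matters. An unconditional floor would silently replace a recorded month or year that really is earlier than diagnosis, and so hide a data error.

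It would also help to state the delay formula in Table 9, including whether 1 day is added.

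The cost is one sentence in the SAP, a short formula in Table 9, about one line of derivation code and a query where the recorded parts conflict. No new data are needed.

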6.9.4. Antineoplastic therapies

Prior Antineoplastic therapies

Incomplete start dates will be handled by applying the same imputation rules as described for AE/concomitant medications start date (Sections 6.9.1 and 6.9.2) except:

- If only day is missing, and month and year match that of the treatment start date, impute as first dose of study -1;
- If both day and month are missing, and the year matches that of the treatment start date, then impute as date of first dose of study drug - 1.

Completely missing start date is imputed as date of first dose of study drug - 1;

Incomplete end dates and dates of progression on the prior antineoplastic therapies will be handled using the following rule:

- If only day is missing, imputed date = min (date of first dose of study drug -1, last day of the month);
- If both month and day are missing, imputed date = min (date of first dose of study drug -1, 31DEC).
- If the end date or the date of progression is not missing and the imputed start date is after the end date or after the date of progression, use the min (end date, date of progression) as the imputed start date.

Post-treatment therapies:

If any, it will be reported as part of the concomitant medications, and handled as specified in Section 6.9.2.

6.10. Appendix 10: Reporting conventions

6.10.1. P-values presentation

Not Applicable

6.11. Appendix 11: Response Evaluation Criteria in Solid Tumors Version 1.1

Taken from Eisenhauer 2009.

6.11.1. Methods of Measurement

All measurements should be recorded in metric notation, using calipers if clinically assessed. All baseline evaluations should be performed as close as possible to the start of study intervention and never more than 28 days before the first dose.

The same method of assessment and the same technique should be used to characterize each identified and reported lesion at baseline and during the treatment phase and follow-up phase (if applicable). Imaging based evaluation should always be done rather than clinical examination unless the lesion(s) being followed cannot be imaged but are assessable by clinical examination.

Clinical lesions: Clinical lesions will only be considered measurable when they are superficial and ≥ 10 mm diameter as assessed using calipers (e.g. skin nodules). For the case of skin lesions, documentation by color photography including a ruler to estimate the size of the lesion is suggested. As noted above, when lesions can be evaluated by both clinical examination and imaging, imaging evaluation should be undertaken since it is more objective and may also be reviewed at the end of the study.

Chest X-ray: Chest CT is preferred over chest X-ray, particularly when progression is an important endpoint, since CT is more sensitive than X-ray, particularly in identifying new lesions. However, lesions on chest X-ray may be considered measurable if they are clearly defined and surrounded by aerated lung.

CT, MRI: CT is the best currently available and reproducible method to measure lesions selected for response assessment. This guideline has defined measurability of lesions on CT scan based on the assumption that CT slice thickness is 5 mm or less. When CT scans have slice thickness greater than 5 mm, the minimum size for a measurable lesion should be twice the slice thickness. MRI is also acceptable in certain situations (e.g. for body scans).

Ultrasound: Ultrasound is not useful in assessment of lesion size and should not be used as a method of measurement. Ultrasound examinations cannot be reproduced in their entirety for independent review at a later date and because they are operator dependent, it cannot be guaranteed that the same technique and measurements will be taken from one assessment to the next. If new lesions are identified by ultrasound in the course of the study, confirmation by CT or MRI is advised. If there is concern about radiation exposure at CT, MRI may be used instead of CT in selected instances.

Endoscopy, laparoscopy: The utilization of these techniques for objective tumor evaluation is not advised. However, they can be useful to confirm complete pathological response when biopsies

Sponsor Name: Pierre Fabre Médicament

Sponsor Protocol ID: W00090GE102

PII

are obtained or to determine relapse in studies where recurrence following complete response or surgical resection is an endpoint.

Tumor markers: Tumor markers *alone* cannot be used to assess *objective* tumor response. If markers are initially above the ULM, however, they must normalize for a participant to be considered in CR. Because tumor markers are disease specific, instructions for their measurement should be incorporated into protocols on a disease specific basis.

Cytology, histology: These techniques can be used to differentiate between PR and CR in rare cases if required by protocol (for example, residual lesions in tumor types such as germ cell tumors, where known residual benign tumors can remain). When effusions are known to be a potential adverse effect of treatment (e.g. with certain taxane compounds of angiogenesis inhibitors), the cytological confirmation of the neoplastic origin of any effusion that appears or worsens during treatment can be considered if the measurable tumor has met criteria for response or stable disease in order to differentiate between response (or stable disease) and progressive disease.

6.11.2. Measurability of Tumour at Baseline

6.11.2.1. Definitions

At baseline, tumor lesions/lymph nodes will be categorized measurable or non-measurable as follows:

- Measurable

Tumor lesions: Must be accurately measured in at least one dimension (*longest* diameter in the plane of measurement is to be recorded) with a *minimum* size of:

- 10 mm by CT scan (CT scan slice thickness no greater than 5 mm).
- 10 mm caliper measurement by clinical examination (lesions which cannot be accurately measured with calipers should be recorded as non-measurable).
- 20 mm by chest X-ray.

Malignant lymph nodes: To be considered pathologically enlarged *and* measurable, a lymph node must be ≥ 15 mm in *short* axis when assessed by CT scan (CT scan slice thickness recommended to be no greater than 5 mm). At baseline and in follow-up, only the *short* axis will be measured and followed.

- Non-measurable

All other lesions, including small lesions (longest diameter < 10 mm or pathological lymph nodes with ≥ 10 to < 15 mm short axis) as well as truly non-measurable lesions. Lesions considered truly non-measurable include leptomeningeal disease, ascites, pleural or pericardial effusion and inflammatory breast disease, lymphangitic involvement of skin or lung, abdominal masses/abdominal organomegaly identified by physical examination that is not measurable by reproducible imaging techniques.

6.11.2.2. Special Considerations Regarding Lesion Measurability

Bone lesions, cystic lesions and lesions previously treated with local therapy require particular comment:

Bone lesions:

- Bone scan, PET scan or plain films are not considered adequate imaging techniques to measure bone lesions. However, these techniques can be used to confirm the presence or disappearance of bone lesions.
- Lytic bone lesions or mixed lytic-blastic lesions, with *identifiable soft tissue components*, that can be evaluated by cross sectional imaging techniques such as CT or MRI can be considered measurable lesions if the *soft tissue component* meets the definition of measurability described above.
- Blastic bone lesions are non-measurable.

Cystic lesions:

- Lesions that meet the criteria for radiographically defined simple cysts should not be considered as malignant lesions (neither measurable nor non-measurable) since they are, by definition, simple cysts.
- 'Cystic lesions' thought to represent cystic metastases can be considered as measurable lesions, if they meet the definition of measurability described above. However, if non-cystic lesions are present in the same participant, these are preferred for selection as target lesions.

Lesions with prior local treatment:

- Tumor lesions situated in a previously irradiated area, or in an area subjected to other loco-regional therapy, are usually not considered measurable unless there has been demonstrated progression in the lesion. Study protocols should detail the conditions under which such lesions would be considered measurable.

6.11.3. Tumor Response Evaluation

To assess objective response or future progression, it is necessary to estimate the *overall tumor burden at baseline* and use this as a comparator for subsequent measurements. Measurable disease is defined by the presence of at least one measurable lesion (see Section 6.11.2.1).

6.11.3.1. Baseline Documentation of 'Target' and 'Non-target' Lesions

When more than one measurable lesion is present at baseline all lesions up to a maximum of five lesions total (and a maximum of two lesions per organ) representative of all involved organs should be identified as *target lesions* and will be recorded and measured at baseline (this means in

Sponsor Name: Pierre Fabre Médicament

Sponsor Protocol ID: W00090GE102

PII

instances where participants have only one or two organ sites involved, a *maximum* of two and four lesions respectively will be recorded).

Target lesions should be selected on the basis of their size (lesions with the longest diameter), be representative of all involved organs, but in addition should be those that lend themselves to *reproducible repeated measurements*. It may be the case that, on occasion, the largest lesion does not lend itself to reproducible measurement in which circumstance the next largest lesion which can be measured reproducibly should be selected.

Lymph nodes merit special mention since they are normal anatomical structures which may be visible by imaging even if not involved by tumor. As previously noted, pathological nodes which are defined as measurable and may be identified as target lesions must meet the criterion of a short axis of ≥ 15 mm by CT scan. Only the *short* axis of these nodes will contribute to the baseline sum. The short axis of the node is the diameter normally used by radiologists to judge if a node is involved by solid tumor. Nodal size is normally reported as two dimensions in the plane in which the image is obtained (for CT scan this is almost always the axial plane; for MRI the plane of acquisition may be axial, sagittal or coronal). The smaller of these measures is the short axis.

For example, an abdominal node which is reported as being 20 mm \times 30 mm has a short axis of 20 mm and qualifies as a malignant, measurable node. In this example, 20 mm should be recorded as the node measurement. All other pathological nodes (those with short axis ≥ 10 mm but < 15 mm) should be considered non-target lesions. Nodes that have a short axis < 10 mm are considered non-pathological and should not be recorded or followed.

A *sum of the diameters* (longest for non-nodal lesions, short axis for nodal lesions) for all target lesions will be calculated and reported as the *baseline sum diameters*. If lymph nodes are to be included in the sum, then as previously noted, only the *short* axis is added into the sum. The baseline sum diameters will be used as reference to further characterize any objective tumor regression in the measurable dimension of the disease.

All other lesions (or sites of disease) including pathological lymph nodes should be identified as *non-target lesions* and should also be recorded at baseline. Measurements are not required and these lesions should be followed as 'present', 'absent' or in rare cases 'unequivocal progression' (more details to follow). In addition, it is possible to record multiple non-target lesions involving the same organ as a single item on the case record form (e.g. 'multiple enlarged pelvic lymph nodes' or 'multiple liver metastases').

